For a subject who experiences a reaction to asparaginase during the infusion and has to switch to Erwinia asparaginase during the induction chemotherapy, it is recommended that the subject continue the study treatment. The percentage of the original asparaginase dose delivered will be collected in the patient chart and case report form.

A platelet count $\geq 20,000$ / μ L must be obtained within 24 hours prior to the first dose of apixaban. A subject may be transfused platelets per investigator's clinical judgment but may not be transfused solely to meet entry criteria.

Apixaban should be discontinued at least 24 hours prior to any planned lumbar puncture (LP) and resumed no sooner than 18-24 hours after the procedure. In the event of a traumatic lumbar puncture (defined in this protocol as a lumbar puncture with ≥ 10 red blood cells (RBCs)/ μ L of cerebrospinal fluid (CSF), apixaban should be held for 48 hours after the procedure.

For example, for a LP scheduled on the morning of Day 8, the Day 7 PM and Day 8 AM and PM doses of apixaban should be held and may be restarted the morning of Day 9. If a subject will receive an LP on Day 29, the last dose will be the AM dose on Day 28.

During the study treatment period, study visits will occur on Day 8 \pm 5 days, Day 15 \pm 5 days, Day 22 \pm 5 days and Day 29 \pm 5 days of planned 3-4 drug systemic induction chemotherapy. Windows for study visits after randomization will be \pm 5 days. The timing of these study visits will coincide with standard of care visits for pediatric subjects in induction chemotherapy. Visits will consist of reporting adverse events (including bleeding and secondary endpoints as described below), monitoring medication adherence and laboratory testing. On the Day 29 visit, imaging evaluation will occur for all randomized subjects except for those who are discontinued from protocol therapy. For those subjects randomized to apixaban, imaging evaluations will be performed within 3 days but no more than 5 days of discontinuing apixaban. For those subjects randomized to the standard of care arm, it would be preferred that the imaging evaluations be performed within three days but no more than 5 days from Day 29 (Day 24 to Day 34). The evaluation will include a) a bilateral Doppler ultrasound that will include imaging of the venous system in which the CVAD is placed and the similar location for the opposite side; and b) an echocardiogram to assess for right atrial

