3.5 Discontinuation of Subjects from Treatment

Subjects MUST discontinue investigational product (and non-investigational product at the discretion of the investigator) for any of the following reasons:

- Withdrawal of informed consent (subject's or guardian's decision to withdraw for any reason).
- Any clinical adverse event (AE), laboratory abnormality or intercurrent illness which, in the opinion of the investigator, indicates that continued participation in the study is not in the best interest of the subject
- Pregnancy
- Termination of the study by Bristol-Myers Squibb (BMS) / Pfizer
- Loss of ability to freely provide consent through imprisonment or involuntary incarceration for treatment of either a psychiatric or physical (eg, infectious disease) illness
- CVAD is lost before the Day 29 ± 5 end-of-study evaluation due to endpoint related events (eg, VTE, serious bleeding)
- Major bleeding event
- Thromboembolic event such as DVT, PE, CVST or arterial thromboembolic event.

In the case of pregnancy, the investigator must immediately notify the BMS Medical Monitor/designee of this event. In most cases, the study drug will be permanently discontinued in an appropriate manner. If the investigator determines a possible favorable benefit/risk ratio that warrants continuation of study drug, a discussion between the investigator and the BMS Medical Monitor/designee must occur.

All subjects who discontinue study drug (ie, are off protocol therapy), including discontinuation due to thromboembolic or major bleeding event, or loss of catheter before the Day 29 \pm 5 end-of-study evaluation because of achieving a primary endpoint, should comply with protocol specified follow-up procedures as outlined in [Section 5](#). Every attempt should be made to have the study-related radiographic procedures, Ultrasound and Echocardiogram performed within 72 hours of the event regardless of receiving apixaban or not, and the telephone or in-person safety assessment completed on Day 35 \pm 5 Days.

If the catheter is to be removed and replaced within 48 hours due to events other than a primary endpoint event (eg, VTE or major bleeding), the subject should not have the study mandated ultrasound and echocardiogram until Day 29 visit and should continue with the study treatment (for temporary apixaban interruptions related to an invasive procedure, see [Table 4.5.2-1](#)).

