
Elevated liver function tests. An AE/SAE should be reported if applicable
	
If at any time during the treatment period a subject's liver function test (LFT) results show: An isolated elevation of either SGPT (ALT)/SGOT (AST) $\geq 10 \times$ ULN AND/OR a direct (conjugated) bilirubin $> 3 \times$ ULN, obtain the following laboratories: ALT, AST, total bilirubin, direct bilirubin, alkaline phosphatase, GGT, CK as soon as possible (ie, within 3 days). If the repeat tests indicate: 1) ALT/AST $< 10 \times$ ULN and conjugated bilirubin $\leq 3 \times$ ULN, study medication may continue. 2) If the repeat ALT/AST $\geq 10 \times$ ULN AND/OR the conjugated bilirubin is $> 3 \times$ ULN, the study medication must be discontinued. The study medication must be discontinued if: Clinical jaundice is present for a subject at any time OR If ALT/AST $\geq 10 \times$ ULN on any two consecutive occasions OR Conjugated bilirubin $> 3 \times$ ULN on any two consecutive occasions. All subjects with an ALT/AST $\geq 10 \times$ ULN or direct bilirubin $> 3 \times$ ULN will be followed weekly until ALT/AST returns to $< 3 \times$ ULN or to baseline, and the conjugated bilirubin returns to $\leq 1.5 \times$ ULN or to baseline. If study medication is discontinued due to elevated ALT/AST OR BILIRUBIN, as defined above, inform the medical Monitor and Study Director and perform the following: -PT, aPTT, fibrinogen to assess liver synthetic function -Abdominal ultrasound, including liver and hepatobiliary system -Hepatitis screen (anti-HAV, HBsAg, anti-HBc, anti-HBs and anti-HCV. Obtain relevant specialist consultation.

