^a Screening visit can occur up to 14 days prior to randomization. It can also occur at the treatment visit (Day 1 - 4±3) as long as the subject is eligible by medical history, clinical exam, and has the laboratory results back to confirm the inclusive parameters.

Table 5.1-2: Study Procedural Outline ACCL1333 / CV185155					
Procedure	During Treatment Days 7 ± 5 For in-patients only	During Treatment Days 8 ± 5, 15 ± 5, 22 ± 5	End of Treatment Day 29 ± 5 or early drug discontinuation^a	Follow-up Visit Day 35 ± 5	Notes
Concomitant Medication Assessment	X	X	X	X	If done on Day 7 do not need to repeat on Day 8
Safety Assessments					
Targeted Physical Examination	X	X	X		Includes organ systems pertinent to the subject's signs, symptoms, or adverse events, eg, assessment of signs of VTE or bleeding. If done on Day 7 do not need to repeat on Day 8
Vital Signs	X	X	X		Heart rate, BP, respiratory rate and temperature If done on Day 7 do not need to repeat on Day 8
Adverse Events Assessment	X	X	X	X	Collection of SAEs begins after signed consent Collection of non-serious AE begins after randomization
Laboratory Tests: CBC with Platelets, ALT, AST, and direct (conjugated) bilirubin	X	X	X		If done on Day 7 do not need to repeat on Day 8
Laboratory Tests during the LP RBC in the CSF		X	X		RBC in the CSF only taken at investigator defined LPs

Table 5.1-2: Study Procedural Outline ACCL1333 / CV185155					
Procedure	During Treatment Days 7 ± 5 For in-patients only	During Treatment Days 8 ± 5, 15 ± 5, 22 ± 5	End of Treatment Day 29 ± 5 or early drug discontinuationa	Follow-up Visit Day 35 ± 5	Notes
In-patient Pharmacokinetic (PK) and anti-Xa sample collection. See Section 5.5	X				For subjects receiving apixaban only. For inpatient, a pre-dose PK and anti-FXa sample may be taken 1 day prior to LP (prior to the day 7 AM dose if LP on day 8) followed by a PK and anti-FXa sample taken 1-4 hr post dose. If the subject is outpatient, follow alternate sample collection procedures.
Alternate PK sample and anti-Xa collection. See Section 5.5		X			For outpatients, random PK and anti-FXa samples may be obtained prior to LP procedures for example during the Day 8 ± 5 visit and during Day 15 ± 5 visits.
Efficacy Assessments					

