Doppler ultrasound			X		The Doppler ultrasound should be performed for both of the ipsilateral (extremity in which the CVAD was placed) and the contralateral sides whenever possible. If there is a difficulty in performing the imaging procedure, Doppler ultrasound from the ipsilateral side alone is acceptable (see Appendix 1 for detailed guidance). It should be performed within 3 days (not exceed 5 days) after termination of the study medication.

Table 5.1-2: Study Procedural Outline ACCL1333 / CV185155					
Procedure	During Treatment Days 7 ± 5 For in-patients only	During Treatment Days 8 ± 5, 15 ± 5, 22 ± 5	End of Treatment Day 29 ± 5 or early drug discontinuation^a	Follow-up Visit Day 35 ± 5	Notes
Echocardiogram			X		Echocardiogram should be performed within 3 days (not exceed 5 days) after termination of the study medication.
Clinical Drug Supplies					
End taking Study Drug			X		Apixaban will start between Day 1 and Day 4±3 of planned 3-4 drug systemic chemotherapy induction and is stopped on Day 29±5. Based on the quantity of the study drug returned by subjects, dosing compliance will be calculated.

a Subjects who discontinue before the end of treatment need to complete all end of study procedures including ultrasound and echo imaging

No study-related procedure may be performed until the subject or their legally acceptable representative has been completely informed of the study, has freely consented to take part in the study, and has signed and dated an informed consent document, and where appropriate assent form, approved by a licensed Institutional Board Review (IRB) or Independent Ethics Committee (IEC). Every attempt should be made to coordinate the study-related visits with the subjects' medical visits.

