Day 29 ± 5 of chemotherapy visit: Local CBC with platelets, ALT, AST, and direct (conjugated) bilirubin, RBC in CSF, adverse event data collection and concomitant therapy assessment will be performed.

On the Day 29 visit, the imaging evaluation will occur for all randomized subjects who remain on protocol therapy. For those subjects randomized to apixaban, imaging evaluations will be performed preferably within 3 days but no more than 5 days of discontinuing apixaban. For those subjects randomized to the standard of care arm, imaging evaluations will be performed within 3 days but no more than 5 days from Day 29 (Day 24 to Day 34). The evaluation will include a bilateral Doppler ultrasound that will include imaging of the venous system in which the CVAD is placed and an echocardiogram to assess for right atrial thrombi according to the protocol guidance in [appendices 1 and 2](#). Subjects will not undergo routine radiologic screening for CVST. (see [Section 5.4.1](#))

Evaluations to be performed at clinical suspicion of VTE or other off protocol therapy criteria including catheter loss: All subjects who discontinue investigational product due to events such as thromboembolic or major bleeding event, or catheter loss before the Day 29 \pm 5 end-of-study evaluation should remain on study. Every effort must be made to confirm a suspected thromboembolic or bleeding event prior to removal from protocol therapy.

Additional clinical and radiologic evaluations prompted by clinical suspicion of any DVT, PE, CVST, arterial thromboembolic events, bleeding or death will be performed at the discretion of the treating clinician; and information from these visits and imaging findings will be captured for study analysis. Management of any asymptomatic or symptomatic events will be according to the local standards of practice. If study medication is discontinued for a suspected VTE event, alternative anti-thrombotic therapy may be initiated per the Investigator's discretion and standard of care.

It is critical for all patients (SOC and apixaban) that every attempt should be made to have the study-related radiographic procedures, Ultrasound and Echocardiogram, performed within 72 hours of the event and the follow-up safety assessment completed on Day 35 \pm 5.

If the catheter is to be removed, it is preferred that the diagnostic imaging procedures be performed prior to the catheter removal.

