5.4.1 Imaging assessment for the study

On Day 29 \pm 3 days, the imaging evaluation will occur **for all** randomized subjects who remain on protocol therapy. **For subjects in the apixaban treatment arm, Doppler ultrasound and echocardiogram should be performed within 3 days (not exceed 5 days) after termination of the study medication including early discontinuation. For those subjects randomized to the standard of care arm, imaging evaluations will be performed within 3 days but no more than 5 days from the Day 29 visit or early discontinuation from the study.**

The evaluation will include a bilateral Doppler ultrasound that will include imaging of the venous system in which the CVAD is placed and an echocardiogram to assess for right atrial thrombi according to the protocol guidance in [appendices 1 and 2](#). The Doppler ultrasound should be performed for both the ipsilateral (extremity in which the CVAD was placed) and the contralateral sides whenever possible. If there is a difficulty in performing the imaging procedure, Doppler ultrasound from the ipsilateral side alone is acceptable (see [Appendix 1](#) for detailed guidance). Subjects will not undergo routine radiologic screening for CVST.

A chest X-ray is not mandated by the study. However, if a chest X-ray has been performed as part of the standard of care, the chest X-ray should be submitted as part of the adjudication package.

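### After an early, permanent, non-endpoint drug stop, the imaging text can leave an apixaban child with only a stop scan while a comparable control child is scanned at Day 29

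*Protocol*

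**What the plan says.** Protocol 5.4.1 gives the two arms different clocks. For apixaban, "Doppler ultrasound and echocardiogram should be performed within 3 days (not exceed 5 days) after termination of the study medication including early discontinuation". For control, the scan falls within 3 days but "no more than 5 days from the Day 29 visit or early discontinuation from the study". The first clock starts when the drug stops; the second starts at Day 29 or at study exit.

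The Day 29 scan itself is restricted. In the Synopsis (Study Design), "imaging evaluation will occur for all randomized subjects except for those who are discontinued from protocol therapy". In the Synopsis Day 29 paragraph, in Section 5.1 and in 5.4.1, "the imaging evaluation will occur for all randomized subjects who remain on protocol therapy". Section 3.5 equates stopping study drug with being off protocol therapy.

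Table 5.1-2 has a single imaging column, "End of Treatment Day 29 ± 5 or early drug discontinuation". Its footnote a reads: "Subjects who discontinue before the end of treatment need to complete all end of study procedures including ultrasound and echo imaging". Section 5.3 adds that the end-of-treatment visit is due at Day 29 ± 5, also after withdrawal for a Section 3.5 reason.

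Some mandatory stops are not endpoint events. Table 4.5.2-1 states: "The study medication must be discontinued if: Clinical jaundice is present for a subject at any time". The same row, and Section 6.6, require a stop for ALT/AST of at least 10 × ULN, or conjugated bilirubin above 3 × ULN, on two consecutive tests. Section 3.5 also lists "Any clinical adverse event (AE), laboratory abnormality or intercurrent illness which, in the opinion of the investigator" makes staying in the study contrary to the child's interest.

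On the analysis side, the SAP's efficacy period runs to the Day 29 visit (6.1). Imaging up to Day 40 is accepted with no earliest day (8.3). A child with no symptomatic event and no scan counts as event-free (7.5.1).

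**The concern.** The primary endpoint includes asymptomatic DVT, which is found mainly by the protocol scan. The arms are comparable only if that scan covers the same span of follow-up in both. Take two children who develop jaundice on Day 10 and stay in the study. The control child has no drug to stop and is scanned around Day 29. The apixaban child must stop the drug and, read as 5.4.1 states it, is scanned by about Day 13-15 with no later scan scheduled. Silent thrombus forming in the following two weeks is looked for in one child and not in the other.

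The direction is fixed: the rule can only lower the observed apixaban rate. The early negative scan can also pass into the analysis as a real observation, a non-event in ITT and an evaluable scan in mITT. The planned multiple imputation and tipping point act only on missing or non-evaluable data, so they leave it alone. Symptomatic events are not affected, because suspected clinical events are adjudicated up to Day 35 ± 5 (Protocol 5.4).

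**Working it through.** **1. The plan's own figures.** Power = Φ[((p_c − p_a) − 1.96·SE0)/SE1], where SE0 uses the pooled rate and SE1 the separate rates.
- 17% v 8.5%, 250 per arm: (0.085 − 1.96 × 0.02983)/0.02959 gives 81.5%.
- 20% v 10%, 200 per arm after the 20% exclusion: (0.10 − 1.96 × 0.03571)/0.03536 gives 80.2%.

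Both match the stated power of more than 80%, so 250 per arm and a 17% control rate are used below.

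**2. Which stops count.**
- *Liver rule:* a required stop with no control counterpart. This is the clearest case.
- *Investigator-judged adverse event:* partly, see the objection.
- *Lumbar-puncture and platelet holds:* interruptions, not included.
- *Endpoint events and catheter loss:* Sections 3.5 and 5.1 ask for imaging within 72 hours in both arms, not included.
- *Stops from about Day 21:* harmless, because a scan 3 days later falls in the Day 24-34 window.

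**3. Assumptions (none is in the documents).** d = share of apixaban children with a permanent non-endpoint stop, 2-10%. Stop on Day 8 or Day 15. Scan 3 days later. VTE accrues evenly over 28 days. s = silent share of events = 0.8. A silent thrombus persists to Day 29.

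**4. Unseen events with no drug effect (17% in both arms).** Unseen points = d × 17 × f × s, with f = (29 − scan day)/28.
- Day 15 stop: f = 11/28 = 0.393. Day 8 stop: f = 18/28 = 0.643.
- Events in 250 children = points × 2.5.
- SE = √(2 × 0.17 × 0.83/250) = 3.36 points.
- One-sided error = 1 − Φ(1.96 − unseen/3.36).

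| d | Unseen points (Day 15 / Day 8 stop) | Events | One-sided error |
|---|---|---|---|
| 2% | 0.107 / 0.175 | 0.27 / 0.44 | 2.69% / 2.82% |
| 5% | 0.267 / 0.437 | 0.67 / 1.09 | 3.00% / 3.36% |
| 10% | 0.534 / 0.874 | 1.34 / 2.19 | 3.59% / 4.46% |

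A simulated age-stratified Cochran-Mantel-Haenszel test (assumed strata of 175 and 75 per arm) agreed to within 0.05 percentage points over this range.

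**5. Varying the inputs.**
- With s from 0.6 to 1.0, the error range is 2.64% to 5.11%.
- With the scan at the 5-day limit and s = 0.8, f falls to 9/28 = 0.321 (Day 15) and 16/28 = 0.571 (Day 8). Unseen events become 0.22 to 1.94 and the error 2.66% to 4.19%.

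**6. At the design rates.** Let risk return to the control level after the stop: true rate = 8.5 + d × 8.5 × (29 − stop day)/28; seen rate = true − unseen.
- d = 2%, Day 15: true 8.585%, seen 8.478%; relative risk 0.505 reads as 0.499.
- d = 10%, Day 8: true 9.138%, seen 8.263%; relative risk 0.538 reads as 0.486.

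**7. When a Day 29 scan beats a stop scan.** A stop scan alone misses share f of silent events. A Day 29 scan that share q of stoppers fail to attend misses q. They break even at q = f: 39% (Day 15 stop) or 64% (Day 8 stop), under even accrual.

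**The case against.** The best reply is that the protocol already asks for Day 29 imaging after a stop. Footnote a requires early discontinuers to complete end-of-study procedures including both scans, elsewhere the protocol calls the Day 29 assessment the end-of-study evaluation, and Section 5.3 sets the end-of-treatment visit at Day 29 ± 5 after a Section 3.5 withdrawal. That stands as a possible reading, and nothing forbids a later scan. It does not settle the matter: the Table 5.1-2 column offers Day 29 or early drug discontinuation, Section 5.3 does not mention imaging, and four places limit the Day 29 scan to children on protocol therapy. Likewise, whether an early scan counts as end-of-study imaging for mITT is a matter of interpretation.

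Three stronger readings are tempting and go too far.

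- *That the loss falls in the apixaban arm only.* The adverse-event criterion in Section 3.5 is worded around staying in the study, which can also apply to a control child, and a control child who leaves the study is scanned early too. The supportable statement is mainly the apixaban arm, with the liver rule as the clean case. Even there, the rule sits in a table of temporary interruptions, Section 4.5.2 allows clinical judgment, and no text bars a restart.
- *That no planned analysis touches these children.* SAP 7.2.1 lists more than 3 consecutive days without apixaban as a relevant deviation, outside protocol-defined interruptions, so the Evaluable analysis would probably drop them. But it runs only if at least 10% of subjects have such a deviation, and it excludes children without recovering their Day 29 status.
- *That the plan's 20% allowance is a stop rate.* It describes missing or non-evaluable scans in the second power scenario. Put in as d, it gives an error of 5.0-7.5%, a stress case with no support in the documents.

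The objection that the size rests on assumption is right.

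**Conclusion.** The point holds as a conflict in the imaging text with a one-directional risk. Where a site follows 5.4.1, silent DVT after a non-endpoint stop can go unseen mainly in the apixaban arm, and SAP 8.3 lets the early negative scan count as an observed non-event.

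The size is unknown. About 0.3-2.2 unseen events and a one-sided error of 2.7-4.5% follow from assumed stop rates, stop days, silent share, even accrual and persistence of thrombus. At 2% stops the effect is negligible; the upper figure needs 10% of apixaban children to stop permanently by Day 8. A reader should not infer that the trial's type I error is inflated to any particular value, or that every stopper goes without a Day 29 scan; the documents support neither. The change is still worth making, because the possible bias always favours the study drug and removing it is cheap.

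**What to change.** **Protocol.** In the Synopsis (Study Design and the Day 29 paragraph), Sections 5.1 and 5.4.1, and the Table 5.1-2 column and footnote a, require the ultrasound and echocardiogram at Day 29 ± 5 in both arms for every child still in the study without a confirmed VTE, whatever the drug status. Use a scan at a non-endpoint stop only as a fallback when the child is not expected to attend Day 29. Keep the 72-hour scan for endpoint events.

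**SAP 8.3 and 7.5.1.1.** In either arm, treat a negative scan before Day 24 with no later scan as missing in the multiple-imputation and tipping-point analyses, and exclude it from mITT. This is a sensitivity check. It does not correct the primary ITT test.

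**Cost.** Wording changes and one SAP rule. The scan is moved rather than added, except for a fallback child who attends Day 29 after all. The downside is that some stoppers may miss the later scan, and SAP 7.5.1 would then count them as event-free. The fallback limits this, and the break-even shares above suggest that the Day 29 scan still sees more unless a large share of stoppers fail to attend. If scanning is already complete, only the SAP check remains.
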